6.1 Study Visits

The schedule of events is summarized in Table 6-1.

Table 6-1
Schedule of Events

Procedure ^a	Screening	Baseline	Treatment Period			EOT	Follow-up	EOS ^b
Visit ^c	1	2	3	4	5	6	7	
Study Day	Day-28 to -1	Day 1 ^d	Day 14 (±3 days)	Day 28 (±3 days)	Day 56 (±3 days)	Day 84 (±3 days)	Day 98 EOT+14 days (±3 days)	Day 112 EOT+28 days (±3 days)
Study Week	0	2	4	8	12	14	16	
GENERAL ASSESSMENTS								
Informed consent	X							
Inclusion/exclusion criteria	X	X						
Demographics	X							
Medical/surgical history	X							
Alcohol and nicotine use	X							
Height	X							
Weight	X	X				X		X
Physical examination ^e	X	X				X		X
Vital sign measurements ^f	X	X	X	X	X	X		X
Adverse event monitoring	X	X	X	X	X	X		X
Concomitant medications	X	X	X	X	X	X		X
Prior medications	X							
RA ASSESSMENTS								
Tender/painful and swollen joint counts (TJC28/SJC28)	X	X	X	X	X	X		X
Physician/patient's global assessments of disease activity ^g		X	X	X	X	X		X
Patient assessment of general health ^h		X	X	X	X	X		X
Patient assessments of arthritis pain ^g		X	X	X	X	X		X

Procedure ^a	Screening	Baseline	Treatment Period			EOT	Follow-up	EOS ^b
Visit ^c	1	2	3	4	5	6	7	
Study Day	Day-28 to -1	Day 1 ^d	Day 14 (±3 days)	Day 28 (±3 days)	Day 56 (±3 days)	Day 84 (±3 days)	Day 98 EOT+14 days (±3 days)	Day 112 EOT+28 days (±3 days)
Study Week		0	2	4	8	12	14	16
HAQ-DL ^g	X	X	X	X	X	X	X	X
Randomization/drug assignment	X							
INVESTIGATIONAL PRODUCT ADMINISTRATION								
Dispense study drug and subject dosing diary		X		X	X	X		
Study drug administration		X	X	X	X	X	X	
Review and copy subject dosing diary and perform drug reconciliation			X	X	X	X		
CENTRAL LABORATORY EXAMINATIONS								
HBsAg, HBCaB, HCV, and HIV tests	X							
QuantiFERON Gold - tuberculosis test ^h	X							
Serum pregnancy test ⁱ	X							
FSH level	X	X						
Urine pregnancy test ⁱ		X	X	X	X	X	X	X
Hematology ^j	X	X	X	X	X	X	X	X
Coagulation	X	X	X	X	X	X	X	X
Chemistry ^j	X	X	X	X	X	X	X	X
Urinalysis	X	X	X	X	X	X	X	X
hsCRP ^k	X	X	X	X	X	X	X	X
IMAGING								
Chest x-ray ^l	X							
12-lead electrocardiogram ^m	X	X	X	X	X	X	X	X
SUBSTUDY								

Procedure ^a	Screening	Baseline	Treatment Period			EOT	Follow-up	EOS ^b
Visit ^c		1	2	3	4	5	6	7
Study Day	Day-28 to -1	Day 1^d	Day 14 (±3 days)	Day 28 (±3 days)	Day 56 (±3 days)	Day 84 (±3 days)	Day 98 EOT+14 days (±3 days)	Day 112 EOT+28 days (±3 days)
Study Week		0	2	4	8	12	14	16
Blood sampling for PK ^e		X	X	X	X	X		
Blood sampling for PD (CD63 + basophils) ^f		X	X	X	X	X		

Abbreviations: ACR, American College of Rheumatology; CD63, cluster of differentiation 63; DAS, disease activity score; EDTA, ethylenediaminetetraacetic acid; EOS, end-of-study; EOT, end of treatment; FSH, follicle-stimulating hormone; HBsAg, hepatitis B surface antigen; HIV, human immunodeficiency virus; HAQ-DI, Health assessment questionnaire disability index; HBcAb, hepatitis B core antibody; HCV, hepatitis C virus; hsCRP, high sensitivity C-reactive protein; PD, pharmacodynamic; PK, pharmacokinetic; PPD, purified protein derivative; RA, rheumatoid arthritis; TB, tuberculosis; WOCBP, women of child bearing potential.

^a When procedures overlap at the same timepoints, the vital parameters assessment will be performed first followed by laboratory parameters and other procedures (Section 6.4.2).

^b Subject who choose to discontinue study treatment, but continue to participate in the study should complete EOT visit as soon possible, preferably within 2 weeks. Afterwards, subjects should follow the regular visit schedule and adhere to all study procedures except for dispensing study drug, and blood sample collection for optional exploratory research and validation studies.

^c Any of the procedures may be performed at an unscheduled visit at the discretion of the investigator.

^d All study procedures on Day 1 must be completed prior to randomization in order to save time for IMP dispensation and postdose PK/PD sampling.

^e A complete physical examination should be performed at the time points specified. Interim physical examinations can be performed at the discretion of the investigator, if deemed necessary to evaluate AEs or clinical laboratory abnormalities (Section 6.4.1).

^f Vital sign measurements include systolic and diastolic blood pressure, pulse rate, respiratory rate, and oral temperature (tympanic temperature for Korean subjects). The subject must be seated for 5 minutes before all measurements are taken (Section 6.4.2).

^g Patient questionnaires and scales should be performed prior to any procedures and assessments. The HAQ-DI should be scored for all 8 categories (Section 6.3.3).

^h TB testing will be performed for all subjects within 28 days of Day 1. Positive diagnostic TB test, which is defined as positive QuantiFERON Gold test will be tested in central laboratories for all subjects and will determine subject's eligibility with regards to TB.

ⁱ For women of child bearing potential (WOCBP), serum pregnancy test performed with screening safety laboratory tests and sent to the central laboratory for processing. To confirm pregnancy, urine pregnancy test will be performed locally on Day 1 prior to randomization and prior to study drug administration on each subsequent visit. If urine pregnancy test is negative, dosing will be started; if urine pregnancy test is positive then withhold dosing and perform a serum pregnancy test. For post-menopausal female subjects, FSH levels will be assessed at screening and baseline to confirm post-menopausal status.

^j Repeat of clinical chemistry and hematology laboratory tests may be allowed once during screening period (after an approval from medical monitor), if the initial result is unexpected/unexplained (not due to a known underlying condition or concomitant medications or other known cause).

^k Repeat of hsCRP test may be allowed once during screening period (after an approval from medical monitor), if the result is considered unexplained/unexpected (eg, not corresponding with clinical disease activity or discordant with recent local result).

^l Chest x-ray must be obtained during the screening period, unless a radiograph was obtained within 12 weeks prior to screening visit.

^m Single 12-lead ECGs will be obtained, after the subject has been in the supine position for at least 5 minutes, prior to randomization at Visit 1 (Section 6.4.3).

ⁿ PK/PD Subset Only: Samples to be collected at the following time points:

Day 1: 0 hour (predose), 15 minutes (PK only +5 minutes), 30 minutes (± 5 minutes), 1 hour, 2, 4, 8, and 12 hours (± 10 minutes) postdose (12 hours sample should be collected prior to the evening dose).

Day 14 (Weeks 2), Day 28 (Week 4), and Day 56 (Week 8): predose samples will be collected prior to the morning dose only.

Day 84 (Week 12): 0 hour (predose), 15 minutes (PK only +5 minutes), and 30 minutes (± 5 minutes), 1 hour, 2, 4, 8, and 12 hours (± 10 minutes) after administration of the morning dose.

PK and PD whole blood samples must be collected using heparin as the anticoagulant. EDTA and citric acid should not be used as anti-coagulants for the collection of these samples. When the PK blood sample collection coincides with safety assessments, PK blood samples should be collected as close to the scheduled time point as possible and safety assessments should be performed before PK blood samples are taken. (Section 6.5.1)

6.2 Demographic and Medical History

Demographic data consisting of age, sex, race, body weight, height, and BMI will be collected at the time points specified in the schedule of events (Table 6-1). A complete medical history (including prior and concomitant medical conditions and procedures; drug, alcohol, and tobacco use) and current/recent medications taken (including use of herbal remedies and vitamin supplements) will be collected at the time points specified in the schedule of events (Table 6-1).

6.3 Efficacy Assessments

Efficacy will be assessed by the evaluation of the mean decrease from baseline in disease activity score in 28 joints (DAS28; individual components, DAS28 [hsCRP]), ACR criteria (individual components; ACR20; ACR50; ACR70), count of tender/painful and swollen joints, global assessment of disease activity (assessed using the visual analog scale [VAS] by physician and subject), subjects assessment of arthritis pain, and health assessment questionnaire-disability index (HAQ-DI) at the time points specified in the schedule of events (Table 6-1).

6.3.1 Disease Activity Score Using 28 Joint Counts

Disease activity score using 28 joint counts (hsCRP) will be evaluated prior to randomization at Visit 1 and at each subsequent visit.

The core set of variables for DAS28 for this study include:

- Number of tender and swollen joints with a total of 28 joints assessed for tenderness and 28 for swelling (Appendix 13.5)
- Subject's global assessment of disease activity (VAS) (Appendix 13.8)
- hsCRP

Note: During the Protocol Amendment 2 dated 08 Feb 2019, the subject's global assessment of disease activity VAS scale was reversed from the standard way they are presented in clinical trials. Scoring of this VAS scale was found to be variable across the sites, since some sites used the reverse scales, while others used the original anchors. Given this inherent

variability, the primary endpoint will now include only the 3 component DAS28-hsCRP, excluding the global assessment of disease activity VAS.

DAS28 based on CRP (DAS28-CRP) may be calculated using 3 or 4 variables.

DAS28-CRP(4) is computed using 4 variables: swollen and tender joint count, CRP, and subject's global assessment of disease activity. DAS28-CRP(3) only includes swollen and tender joint count and CRP as subject global assessment has been excluded. DAS28-CRP(3) may seem more feasible than DAS28-CRP(4) as it does not include subject global assessment, therefore it may be less influenced by subject's mood, etc., and may be considered a more reliable measure of disease activity. Baseline and 4 months disease activity data from 239 rheumatoid arthritis patients treated with a biological agent were extracted from the Danish registry for biological treatment in rheumatology (DANBIO). DAS28-CRP(4) at baseline was 4.8 ± 1.2 versus 4.6 ± 1.1 for DAS28-CRP(3). After 4 months of biological treatment, the scores for DAS28-CRP(4) and DAS28-CRP(3) had improved by -1.39 ± 1.34 ($p < 0.0001$) and -1.18 ± 1.22 ($p < 0.0001$), respectively. It was concluded that the thresholds for low and high disease activity and for improvements were the same for the 2 scores. While DAS28-CRP(3) yielded lower scores, categorized less patients as having high disease activity level, and scores may differ in individual subjects, and was less sensitive to change than DAS28-CRP, the 2 DAS-scores were highly correlated at both baseline ($r = 0.96$, $p < 0.0001$) and at 4 months ($r = 0.97$, $p < 0.0001$). Hence, DAS28-CRP(3) and DAS28-CRP(4) agree well on group level that are relevant for analysis of group-level data in a clinical trial setting (Madsen 2011).

A sensitivity analysis will also be performed using the 4 components DAS28-hsCRP on these subjects. The clinical team will determine on a subject by subject basis how the subject's global assessment of disease activity VAS in the DAS28-hsCRP from each subject was scored, and identify subjects who consistently completed the subject's global assessment of disease activity reverse VAS scale to include in this analysis. Only subjects who completed this VAS scale in a consistent manner throughout the study will be included in this analysis; other subjects will be excluded. For subjects who will be included in this analysis using the reversed scale, the values collected will be changed using 100 minus the original value to determine the final score to be used in the analysis. The details of the subjects who will be included for this sensitivity analysis will be provided in a separate document.

The joint counts will be completed by an Independent Joint Assessor who is not responsible for the primary care of the subjects. The Independent Joint Assessor should be a qualified medical professional (eg, nurse, physician's assistant, physician). Any other joint assessor must be trained (eg, GRAPPA training) and competent in performing such assessments. It is the responsibility of the Investigator to ensure that all assessors are qualified and trained to perform joint assessment. Independent Joint Assessors should be listed in the Delegation of Authority.

6.3.2 American College of Rheumatology Criteria and Individual Components

The ACR criteria are a series of individual assessments used for the calculation of ACR20, ACR50, and ACR70. The ACR criteria will be evaluated from Visit 2 onwards till EOS. The ACR core set of variables (individual components) for this study include:

- Number of tender and swollen joints with a total of 68 joints assessed for tenderness and 66 for swelling
- Subject's assessment of pain using visual analog scale (VAS) (Appendix 13.7)
- Subject's and physician's global assessment of disease activity (VAS) (Appendix 13.8)
- HAQ-DI estimate of physical ability (Appendix 13.10)
- hsCRP

The joint counts will be completed by an Independent Joint Assessor who is not responsible for the primary care of the subjects. The Independent Joint Assessor should be a qualified medical professional (eg, nurse, physician's assistant, physician). Any other joint assessor must be trained (eg, GRAPPA training) and competent in performing such assessments. It is the responsibility of the Investigator to ensure that all assessors are qualified and trained to perform joint assessment. Independent Joint Assessors should be listed in the Delegation of Authority.

6.3.3 Health Assessment Questionnaire-Disability Index

The HAQ-DI will be completed by the subject prior to randomization at Visit 1 and at each subsequent visit as specified in the schedule of events (Table 6-1).

There are 8 categories in HAQ-DI: dressing and grooming, arising, eating, walking, hygiene, reach, grip, and activities. Scoring for each category is from 0 (without any difficulty) to 3 (unable to do). The highest score reported by the subject for any component question of the 8 categories determines the score for the category. If an aid/device or help is required from another individual, then the minimum score for that category will be 2. If the section score is already 2 or more, then no modification will be made.

If an item does not apply to subject (eg, they don't shampoo their hair, take tub baths, or reach for a heavy object above their heads), they should leave the item(s) blank since the purpose is to obtain data about what they can do.

If a component question is left blank or the response is too ambiguous to assign score, then the score for the category will be determined by the remaining completed question(s).

If all component questions are blank or if more than one answer is given, then the subject should be followed up.

If subject's mark is between the response columns, then score will be moved with the closest one. If subject's mark is directly between two response columns, score will be moved with the higher one.

Each of the disability items on the HAQ has a companion aids/devices variable that is used to record what types of assistance, if any, the subject uses for performing usual activities. If no aids, devices, or help is used, subject will leave those questions blank.

The aids and devices are assigned to the specific HAQ sections as follows:

- Dressing and Grooming: devices used for dressing (button hook, zipper pull, shoehorn, etc.)
- Arising: special or built up chair
- Eating: built up or special utensils
- Walking: cane, walker, crutches, wheelchair
- Hygiene: bathtub bar, long-handled appliances in bathroom, raised toilet seat
- Reach: long-handled appliances for reach

- Grip: jar opener for previously opened

These variables are scored as:

- 0 = no assistance
- 1 = special device is used by subject for usual activities
- 2 = subject needs help from another person
- 3 = subject usually needs both a device and help from another person

For more detailed guideline and examples refer to Appendix 13.10.

6.4 Safety Assessments

Safety variables will include physical examination findings, vital sign measurements (systolic and diastolic blood pressure, pulse rate, respiratory rate, and oral temperature [tympanic temperature for Korean subjects]), ECG tracings, clinical laboratory test results (hematology, coagulation, serum chemistry, urinalysis, and urine pregnancy test), weight, body mass index, and reporting of AEs.

Safety assessments will be conducted as shown in the schedule of events (Table 6-1).

6.4.1 Physical Examination

A complete physical examination will be performed at screening, Day 1, EOT (Visit 5), and EOS (Visit 7) as indicated in the schedule of events (Table 6-1).

A complete physical examination will include assessments of general appearance; head, ears, eyes, nose, and throat (HEENT); chest and lungs; cardiovascular; abdomen (gastrointestinal); skin (including nails and hair); lymph nodes; psychiatric/emotional; neurological; and musculoskeletal.

Interim physical examinations can be performed at the discretion of the investigator, if deemed necessary to evaluate AEs or clinical laboratory abnormalities.

6.4.2 Vital Sign Measurements, Height, and Weight

Vital sign measurements will include systolic and diastolic blood pressures, pulse rate, respiratory rate, and oral temperature (tympanic temperature for Korean subjects). The subject must be seated for at least 5 minutes before all measurements are taken.

Vital signs will be measured at screening and other visits as indicated in the schedule of events (Table 6-1).

Height will be measured at screening only. Weight will be measured at screening, Day 1 (Visit 1), and EOS (Visit 7).

When procedures overlap at the same timepoints, the vital parameters assessment will be performed first followed by laboratory parameters and other procedures.

The Investigator will determine whether any of the vital sign measurements are clinically significant or not clinically significant. Clinical significance is defined as any variation in results that has medical relevance and may result in an alteration in medical care (eg, active observation, diagnostic measures, or therapeutic measures).

If a clinically significant change from the screening value is noted, the clinically significant value and the reason for clinical significance will be documented on the AE page of the subject's eCRF. The Investigator will continue to monitor the subject with additional assessments until the value has reached either the reference range, the value at screening, or until the Investigator determines that follow-up is no longer medically necessary.

6.4.3 Electrocardiograms

Single 12-lead ECGs will be obtained, after the subject has been in the supine position for at least 5 minutes, prior to randomization at Visit 1 and at subsequent visit as indicated in the schedule of events (Table 6-1). Electrocardiogram assessments will include comments on the rhythm; presence of arrhythmia or conduction defects; morphology; or ST segment, T wave, and U wave abnormalities; whether the tracings are normal or abnormal and whether there is any evidence of myocardial infarction. In addition, the following parameters will be measured and reported: RR interval, PR interval, QRS width, QT interval, and corrected QT interval from Fridericia's formula (QTcF).

The Investigator will determine whether any of the 12-lead ECG results are normal or abnormal and whether any abnormal results are clinically significant or not clinically significant. Clinical significance is defined as any variation in results that has medical relevance and may result in an alteration in medical care (eg, active observation, diagnostic measures, or therapeutic measures).

If a clinically significant change from screening is noted, the clinically significant value and the reason for clinical significance will be documented on the AE page of the subject's eCRF. The Investigator will continue to monitor the subject with additional assessments until the values have reached either the reference range or the values at screening or until the Investigator determines that follow-up is no longer medically necessary.

If ECG tracings are printed on a thermal paper, a certified copy must be made, attached to the original, and filed in the subject's records to ensure results remain clear and legible over time.

6.4.4 Clinical Laboratory Tests

Clinical laboratory tests required for the study will be performed by PPD's central laboratory (except for the urine pregnancy test performed locally from Visits 1 to 7). For adverse event assessment and support, local laboratory results may be used.

Blood (hematology, coagulation, chemistry, hsCRP) and urine (urinalysis and urine pregnancy test) samples will be collected at screening, prior to randomization at Visit 1, and at each subsequent visit as indicated in the schedule of events (Table 6-1). Repeat of hsCRP may be allowed once during screening period (after an approval from medical monitor), if the result is considered unexplained/unexpected (eg, not corresponding with clinical disease activity or discordant with recent local result). Repeat of clinical chemistry and hematology laboratory tests may be allowed once during screening period (after an approval from medical monitor), if the initial result is unexpected/unexplained (not due to a known underlying condition or concomitant medications or other known cause).

The following assessments will be performed at screening only to determine eligibility:

- HBsAg, HBcAb, HCV, and HIV tests
- For WOCBP, serum pregnancy test performed with baseline safety laboratory tests and sent to the central laboratory for processing.

For WOCBP, to confirm pregnancy, urine pregnancy test will be performed locally on Day 1 prior to randomization and prior to study drug administration on each subsequent visit as indicated in the schedule of events (Table 6-1). If urine pregnancy test is negative, dosing will be started; if urine pregnancy test is positive then site staff must withhold dosing and perform a confirmatory serum pregnancy test.

For post-menopausal female subjects, FSH levels will be assessed at screening and on Day 1 (baseline) prior to randomization to confirm post-menopausal status.

The following hematology, coagulation, serum chemistry, and urinalysis assessments will be performed at all timepoints:

Hematology: Hematocrit, hemoglobin, mean corpuscular hemoglobin, mean corpuscular hemoglobin concentration, mean corpuscular volume, platelet count, red blood cell count, total and differential (absolute and percent) leukocyte count, and erythrocyte sedimentation rate

Coagulation: International normalized ratio, partial thromboplastin time, and prothrombin time

Serum ALT, albumin, alkaline phosphatase (ALP), amylase, anion gap, AST,

Chemistry: bicarbonate, bilirubin (total and direct), blood urea nitrogen, calcium, chloride, cholesterol (total, high-density lipoprotein, and calculated low-density lipoprotein), creatine phosphokinase, creatinine, gamma-glutamyltransferase, globulin, glucose, lactate dehydrogenase, magnesium, phosphorus, potassium, sodium, total protein, triglycerides, troponin I, uric acid, and C-reactive protein

Urinalysis: Appearance, bilirubin, color, glucose, ketones, leukocyte esterase, microscopy (performed if dipstick is positive; includes bacteria, casts, crystals, epithelial cells, red blood cells, and white blood cells), nitrites, occult blood (for urine microscopy), pH, protein, specific gravity, and urobilinogen

Pregnancy: Urine dipstick pregnancy test except at screening

In cases of abnormal urinalysis results, urine microscopy will be performed.

Abnormal clinical laboratory values will be flagged as either high or low (or normal or abnormal) based on the reference ranges for each laboratory parameter. The Investigator will determine whether any abnormally high or low results are clinically significant or not clinically significant. Clinical significance is defined as any variation in results that has medical relevance and may result in an alteration in medical care (eg, active observation, diagnostic measures, or therapeutic measures).

If a clinically significant change from the screening value is noted, the clinically significant value and the reason for clinical significance will be documented on the AE page of the subject's eCRF, even if asymptomatic. The Investigator will continue to monitor the subject with additional assessments until the values have reached either the reference range or the values at screening or until the Investigator determines that follow-up is no longer medically necessary.

The US Food and Drug Administration (FDA) guidance for industry on Drug-Induced Liver Injury: Premarketing Clinical Evaluation (July 2009) will be used as a guideline for the assessment of liver enzymes/liver function tests (DHHS 2009).

Clinically significant laboratory values for individual subjects will be listed. A summary for the numbers and percentages of subjects with clinically significant laboratory values at any time point will be presented.

All laboratory specimen (clinical and bioanalysis) analysis, details in storage and shipment will be followed according to the laboratory manual.

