4.1.1 Inclusion Criteria

Each subject must meet all the following criteria to be enrolled in this study:

1. Subject is an adult male or female aged ≥ 18 years old at time of signing the informed consent (or per local customs for ≥ 19 years of age for Korean subjects).
2. Subject has Body Mass Index (BMI) of ≥ 18 and $< 40 \text{ kg/m}^2$ at screening.
3. Subject who has a diagnosis of RA according to the 1987 ACR criteria (Appendix 13.2) or the 2010 ACR/EULAR classification criteria (Appendix 13.3) for at least 6 months prior to Day 1.
4. Subject has active disease at screening and baseline following treatment of RA with inadequate response to csDMARDs or anti-TNF α biological agent(s) as per 2012 update of the 2008 ACR RA treatment recommendations (Singh JA 2012).
 - a. Active disease is defined as:
 - presence of ≥ 5 swollen joints (of 28 assessed) and presence of ≥ 5 tender joints (of 28 assessed), and
 - serum hsCRP concentration $\geq 0.6 \text{ mg/dL}$ (or $\geq 6.0 \text{ mg/L}$; $1 \text{ mg/L} = 9.524 \text{ nmol/L}$) at screening (based on the upper limit of normal [ULN] of laboratory normal

range). Repeat may be allowed once during screening period (after an approval from medical monitor), if the result is considered unexplained/unexpected (eg, not corresponding with clinical disease activity or discordant with recent local result).

b. At least ONE of the following treatments for RA must have been received:

- anti-TNF α biological agent(s): Includes at least 1 of the following treatments, with completed washout period indicated prior to Day 1 dosing

adalimumab (Humira $^{\circledR}$)	60 days washout
etanercept (Enbrel $^{\circledR}$)	30 days washout
infliximab (Remicade $^{\circledR}$)	60 days washout
certolizumab pegol (Cinzia $^{\circledR}$)	60 days washout
golimumab (Simponi $^{\circledR}$)	60 days washout

- csDMARD therapy: Includes at least 1 of the following dosing regimen for at least 90 days of continuous use (prior to Day 1 dosing)*

- MTX 15 to 25 mg/week. If the current MTX dose is <15 mg/week, the subject's intolerance to \geq 7.5 mg dose must be documented in the subject's medical history
 - \leq 3000 mg/day (3 g/day) sulfasalazine
 - \leq 400 mg/day hydroxychloroquine
 - \leq 200 mg/day minocycline
 - \leq 20 mg/day leflunomide

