5.6 Blinding

This is a double-blind study. Neither the subjects nor the investigator/site personnel will be aware of the treatment assignment for the subjects in each cohort. Additionally, the study drugs will be identical in number and appearance for each cohort. Blinding will be maintained throughout the study by use of active or placebo dosage forms of similar appearance.

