7.2 Secondary Endpoints

Secondary endpoints will be evaluated at Weeks 2, 4, 8 and 12 unless otherwise stated.

- Percentage of subjects who would achieve ACR20, ACR50 and ACR70 response over time
- Change from baseline in DAS28-hsCRP score (based on 3 individual components including TJC, SJC, and hsCRP)
- Change from baseline in the tender/painful and swollen joint count (28)
- Change from baseline in the physician global assessment of disease activity by VAS
- Change from baseline in the subject global assessment of disease activity by VAS
- Change from baseline in the subject's assessment of arthritis pain by VAS
- Change from baseline in the HAQ-DI
- Change from baseline in median hsCRP values at each visit
- Safety and tolerability of SKI-O-703 compared to placebo including laboratory tests, infections, ECGs, vital signs, incidence of AEs, withdrawals due to AEs and serious adverse events (SAEs).
- PK parameters of SKI-O-592 and its metabolites (M2 and M4) from a subset of subjects per cohort on Day 1 and at Week 12, including: Cmax, Tmax, AUC0-tau, t1/2, Kel, CL/F (SKI-O-592 only), Vz/F (SKI-O-592 only), Rmet, and RAUC, as applicable
- PD parameters for the change from baseline in the percentage of activated gp53/CD63+ basophils in peripheral blood on Day 1 and at Week 12, including: Emax, TEmax, AUEC0-tau, as applicable

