8.2. Primary Efficacy Endpoint

The primary efficacy endpoint is the mean change from baseline in DAS28-hsCRP at Week 12, which is based on three individual components including TJC28, SJC28 and hsCRP (see calculation in [Section 8.1.1](#))

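### Protocol 6.4.4 runs CRP and ESR as safety tests at every visit, and neither document withholds post-baseline CRP, hsCRP or ESR from the investigator, the physician scoring the global VAS, or the joint assessor

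*Protocol*

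**What the plan says.** Protocol 6.4.4 introduces its panels with "The following hematology, coagulation, serum chemistry, and urinalysis assessments will be performed at all timepoints". The hematology list closes with "total and differential (absolute and percent) leukocyte count, and erythrocyte sedimentation rate" and the chemistry list with "triglycerides, troponin I, uric acid, and C-reactive protein". The same section and Table 6-1 list hsCRP as a separate sample. Out-of-range values are flagged, and "The Investigator will determine whether any abnormally high or low results are clinically significant or not clinically significant". No analyte is exempted.

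hsCRP is also an efficacy variable. SAP 8.2 describes the primary endpoint as one "which is based on three individual components including TJC28, SJC28 and hsCRP", and SAP 8.1.2 makes hsCRP one of the five ACR items that accompany the joint counts. The physician global VAS is another of those five. It is also a secondary endpoint in its own right (Protocol 7.2: "Change from baseline in the physician global assessment of disease activity by VAS").

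On the blind, Protocol 5.6 says that subjects, investigator and site personnel do not know the assignment, and that "Blinding will be maintained throughout the study by use of active or placebo dosage forms of similar appearance". Protocol 6.3.1 and 6.3.2 give the joint counts to an Independent Joint Assessor outside the subject's primary care. Protocol 3.1 has patients complete their own scales before site contact.

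**The concern.** A blinded rater should not hold on-treatment information that tracks the expected drug effect. CRP is such information here, because it is itself part of the primary score. If the drug lowers CRP, a site that watches the value fall, or stay up, has grounds for a guess at allocation, and that guess may colour a later subjective rating.

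The physician global is most open to this. It is a single judgement on a line, made repeatedly, and no rule in either document governs what the physician may know when making it. A shifted physician VAS feeds the secondary endpoint directly and can tip an ACR20, ACR50 or ACR70 classification. Joint counts also call for judgement, so the primary endpoint would be touched if the joint assessor knew the CRP course.

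**Working it through.** The plan gives no figure on this point, so the check is mainly a comparison of passages.

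1. **Are the results generated?** Yes. ESR, CRP and hsCRP are each measured at every visit (Protocol 6.4.4, Table 6-1).
2. **Does the plan send them to the site?** It requires the investigator to judge abnormal values, with no exception for these tests. Protocol 6.9 excuses findings due to the underlying disease from adverse event reporting, but the investigator has to see a value to make that call. The duty covers abnormal values, not all values.
3. **Will CRP often be abnormal?** Probably at the start. Entry needs hsCRP of at least 6.0 mg/L, a cut-off applied "at screening (based on the upper limit of normal [ULN] of laboratory normal" range). ESR has no entry threshold, so this does not extend to ESR.
4. **Could results arrive in time to matter?** Ratings fall at baseline and Weeks 2, 4, 8 and 12, so the gaps are two to four weeks. A same-visit central result would probably not be back when the rating is made (assumption), but the Week 8 result could be known before the Week 12 rating.
5. **Does any safeguard close this route?**
   - IxRS allocation with an undisclosed block size (Protocol 5.1), blinded pharmacy and clinic staff (5.2) and restricted code-breaking (5.6.1) protect the allocation code. They do not cover inference from a result.
   - The patient-scales-first rule covers the patient's own scales. A footnote in Table 6-1 also marks the row that includes the physician global, but it speaks of patient scales. It orders events within a visit and does nothing about earlier visits' results.
   - The joint assessor must be outside primary care, but is not barred from laboratory results.
   - SAP 8.1.7 lets local hsCRP results obtained because of the pandemic into the primary analysis, without saying who may see them. The sensitivity analysis in SAP 8.2.4 drops those values, but it does not address what raters knew.
6. **Which endpoints are exposed?**
   - Physician global VAS: directly.
   - ACR responses: partly. The physician VAS is one of five items, of which three must improve, in addition to both joint counts (SAP 8.1.2).
   - DAS28-hsCRP(3): only through the joint counts. hsCRP is a laboratory value, and the physician VAS is not in the score.

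**How informative is CRP?** With joint counts held fixed, SAP 8.1.1 gives a score change of 0.36 × 1.10 × ln[(a+1)/(b+1)] for a fall in hsCRP from a to b mg/L. The hsCRP values below are assumed:

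- 20 to 10: 0.396 × ln(21/11) = 0.256, which is 32% of the 0.80 planning difference (0.256/0.80).
- 20 to 5: 0.396 × ln(21/6) = 0.496, or 62%.
- 6 to 3: 0.396 × ln(7/4) = 0.222, or 28%.

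These are the direct contributions of a CRP change to the score. They show that a change of a size relevant to the endpoint would be plain on a laboratory report. They do not measure rater bias.

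**The case against.** Several stronger readings are tempting, and the documents do not support them.

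- *A reader might infer from Protocol 5.6 that the blind rests on matching capsules alone.* It does not. Concealed allocation, blinded staff, an independent joint assessor, patient scales completed first, and blinding until database lock (SAP 4.4) all stand.
- *A reader might infer that the physician scoring the VAS does see CRP.* SAP 8.1.5 says only that a physician scores it. Neither document equates that person with the investigator who reviews laboratory results, or separates the two. Neither says when results return.
- *A reader might infer that CRP reveals the assignment, or that one CRP effect is counted twice.* CRP allows a guess at most. Background csDMARDs and glucocorticoids may continue (Protocol 5.8.1), and CRP may vary on placebo too. No readable passage reports that the drug lowers CRP; that is an expectation from its anti-inflammatory action. Joint counts, CRP and global scores all reflect the same disease, so movement together is not evidence of bias.

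Two further objections carry weight. First, masking might be set out in the laboratory manual or in the assessment appendices, which were not available. The protocol cites the manual for specimen analysis, storage and shipment, so masking there cannot be ruled out. Second, CRP and ESR may have a safety use: infections are a named safety endpoint (Protocol 7.2), immune effects are a listed potential risk (1.5), and there is no safety or data monitoring committee (6.7, 11.1.1). That is a real cost of withholding them. It is limited, because neither the dose-interruption guidance in Table 3-1 nor the adverse events of special interest in 6.4.5.6 uses CRP or ESR, and 6.4.4 allows local results for adverse event assessment.

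**Conclusion.** The gap is real and limited. As written, the plan generates CRP, hsCRP and ESR at every visit, requires review of abnormal values at the site, and withholds post-baseline results from nobody. The physician rating may be influenced by earlier visits' values. The main exposure is the physician global VAS and the ACR responses. The primary endpoint is exposed only if the joint assessor learns the results, which nothing forbids and nothing suggests will happen.

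The size of any bias cannot be quantified from the documents. The conclusion assumes that central results reach the site between visits, that the drug affects CRP, and that the unseen manual and appendices contain no masking rule. The case for acting is that the correction is specific and cheap, not that bias has been shown.

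**What to change.** 1. Remove C-reactive protein from the routine chemistry panel in Protocol 6.4.4. hsCRP is already collected, so no endpoint data are lost.
2. Have the central laboratory withhold hsCRP and ESR results from samples after Day 1 from site staff and efficacy assessors until database lock, and say so in Protocol 5.6 and 6.4.4.
3. State that any local CRP or hsCRP, whether obtained for pandemic reasons or to assess an adverse event, is not shown to the joint assessor or to the physician scoring the VAS. Where one physician would both order the test and score the VAS, the site needs a second rater or a record of the exposure.
4. If the laboratory manual already contains such masking, cross-reference it in the protocol.

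The cost is a central-laboratory reporting change and a short amendment. The downside is that routine CRP and ESR leave the site safety report; local testing for adverse events stays available. If the sponsor prefers to keep these results visible for safety, the protocol should say so and justify the exposure.
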